## 4.3.4. Vital Signs

Summary statistics for vital signs and weight will be presented overall for all patients in the SAF Population for all scheduled visits. Actual values and changes from Baseline will be summarized for all visits where collected.

## 4.3.5. Physical Examination Findings

Physical examination findings at each scheduled visit will be summarized overall for all patients in the SAF Population. The number and percent of patients with abnormal findings by body system will be tabulated.

## 4.3.6. Medications

All prescriptions or over-the-counter medications continued at the start of the trial or started during the trial, and different from the study drug will be recorded. All of these medications will be coded, using WHO Drug Dictionary (March 2014). The use of another version will not be considered a violation of the SAP, nor require an amendment to the plan. Both the coded terms and verbatim terms will be presented in data listings for:

• Concomitant procedures (procedures are not coded)

- Previous and Concomitant medications
- OBR medications
- ART medications

## 4.4. Efficacy

As described in section 3.3.3 of this document, the MEF technique will be applied to the efficacy analyses with regard to imputing missing viral load results as applicable. Note: Prior to calculating change from Baseline in viral load, the log10 value of each measurement will be calculated and will be rounded to one decimal point.

## 4.5.1. Primary Efficacy Endpoint

Per the protocol, the primary efficacy endpoint for the Cohort 2 patients is defined as the proportion of patients achieving  $a \ge 0.5 \log_{10}$  decrease in viral load from Baseline at Day 7 on study drug. A 95% confidence interval around the observed rate will be presented. This endpoint will be presented for all Cohort 2 patients, as well as stratified by:

- 1) Sex (Male vs Female)
- 2) Age (<50 vs > 50)
- 3) Race (Caucasian, Asian, and Other)

The primary efficacy endpoint will not be analyzed for the TMB-301 and TMB-202 rollover patients, as they did not have dosing or viral load measurements at Day 7 on study drug in the TMB-311 study.

## 4.5.2. Secondary Efficacy Endpoints

Although the TMB-311 protocol indicates the secondary efficacy endpoints would only be performed for the Cohort 2 patients, for completeness all secondary efficacy endpoints will be assessed for all patients in all cohorts at applicable visits.

#### 4.5.2.1 HIV-1 RNA levels (copies/mL)

The frequency and proportion of patients achieving RNA levels < 50 copies/mL and < 400 copies/mL along with 95% confidence intervals around the observed rate will be presented at all key visits [Day 7 (Cohort 2 only), and Weeks 24, 48, 72, 96, 120, and 144/EOS] where assessed.

Summary statistics for the actual and change from Baseline of RNA levels will be presented for at all visits where assessed.

## 4.5.2.2 Viral Load (log10 copies/mL)

The frequency and proportion of patients achieving a  $\geq 0.5 \log_{10}$  and  $\geq 1.0 \log_{10}$  decrease from Baseline in viral load along with 95% confidence intervals will be performed at all key visits [Day 7 (Cohort 2 only), and Weeks 24, 48, 72, 96, 120, and 144/EOS] where assessed. The mean change from Baseline at all assessment time points will be presented.

These tables will be repeated for patients receiving an investigational agent [Fostemsavir (BMS-068), Cabotegravir, or PRO140] as a concomitant medication versus those patients who did not receive an investigational agent.

## 4.5.2.3 Virologic Outcome

## Snapshot Approach

Virologic outcome will be assigned for each patient at each key visit after Week 12 [Weeks 24, 48, 72, 96, 120, and 144/EOS], per the snapshot approach, using the following standard categories:

- 1=Virologic success (≥0.5 log10 decline from Baseline in viral load)
- 2a=(<0.5 log10 copies/mL drop from Baseline in viral load)
- 2b=Discontinued efficacy portion of study because of virologic failure (may still continue safety)
- 2c=Discontinued because of other reasons and the drop from baseline in viral load at the time of discontinuation was <0.5 log10 copies/mL
- 2d=OBR changed
- 3a=Discontinued because of AE or death
- 3b=Discontinued because of other reasons and the drop from baseline in viral load at the time of discontinuation was >=0.5 log10 copies/mL
- 3c=Missing data during the window but on study

## Other Virologic Outcomes

Other virologic outcomes will also be defined as follows:

## Failure to achieve/maintain response:

Patient does not have  $\ge 0.5 \log_{10}$  decline from baseline (BL) by Week 12 on study drug OR patient has a  $0.5 \log_{10}$  decline from BL prior to Week 12 but fails to maintain the  $0.5 \log_{10}$  decline from BL and does not have a  $\ge 1 \log_{10}$  increase from nadir on any two consecutive scheduled efficacy assessments after achieving the  $\ge 0.5 \log_{10}$  decline from BL.

#### Rebound:

Patient has a  $\geq 0.5 \log 10$  decline from BL by Week 12 but viral load remains >=50 copies (not suppressed), followed by  $\geq 1 \log_{10}$  increase from nadir at two consecutive scheduled visits any time after achieving the  $\geq 0.5 \log_{10}$  decline from BL.

## **Breakthrough:**

Patient has suppressed viral load (< 50 copies) at any time after primary endpoint followed by ≥200 copies at two consecutive scheduled efficacy assessments.

## **Suboptimal Response:**

Patient has a  $\geq 0.5 \log_{10}$  decline but does not suppress (< 50 copies) at any time after primary endpoint and does not have a  $\geq 1 \log_{10}$  increase from nadir on any two consecutive scheduled efficacy assessments after achieving the  $\geq 0.5 \log_{10}$  decline from BL.

## **Virologic Suppression:**

Patient has a  $\ge 0.5 \log_{10}$  decline and does suppress (< 50 copies) at any time after primary endpoint and does not have a  $\ge 1 \log_{10}$  increase from nadir on any two consecutive scheduled efficacy assessments after achieving the  $\ge 0.5 \log_{10}$  decline from BL.

A table summarizing virologic outcome at the each key visit after Week 12 [Weeks 24, 48, 72, 96, 120, and 144/EOS] according to the above categories will be provided. A listing indicating the virologic outcome for each patient will be included.

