#### At EOS

Treatment	Patient ID	Visit [1]	Visit Date (Study Day)			
				Virologic Outcome [2]	Virologic Failure [3]	Virologic Success [4]
C1:301/800mg	311-XX-XXX	XXXXXXX	DDMONYYYY (XX)	XX	XXXXXXX	XXXXXX
C2:800mg	311-XX-XXX	XXXXXXX	DDMONYYYY (XX)	XX	XXXXXXX	xxxxxx

[1] Visits are assigned based on study day using the windows defined in the statistical analysis plan.

[2] Per the Snapshot Approach:

1=Virologic success (=0.5 log copies/mL drop from Baseline in viral load)

2a=(<0.5 log copies/mL drop from Baseline in viral load)

2b=Discontinued because of virologic failure

2c=Discontinued because of other reasons and drop from baseline in viral load at the time of discontinuation was <0.5 log copies/mL

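### The five other virologic outcomes in SAP 4.5.2.3 are neither exclusive nor exhaustive, so the listing can show a late responder as both virologic failure and virologic success

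*SAP*

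**What the plan says.** SAP 4.5.2.3, under Other Virologic Outcomes, defines five labels:

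- **Failure to achieve/maintain response** has two limbs. The first applies to a patient without a ≥0.5 log10 "decline from baseline (BL) by Week 12 on study drug OR patient has a" (the last words open the second limb). The second applies to a patient with a 0.5 log10 "decline from BL prior to Week 12 but fails to maintain the" decline and has no ≥1 log10 rise from nadir at two consecutive assessments.
- **Rebound** needs a ≥0.5 log10 "decline from BL by Week 12 but viral load remains >=50 copies (not suppressed), followed by" a ≥1 log10 rise from nadir at two consecutive visits.
- **Breakthrough**: "Patient has suppressed viral load (< 50 copies) at any time after primary endpoint followed by ≥200 copies at two consecutive" scheduled assessments. It has no log-rise condition.
- **Suboptimal Response** needs a ≥0.5 log10 "decline but does not suppress (< 50 copies) at any time after primary endpoint and does not have a" ≥1 log10 rise from nadir at two consecutive assessments.
- **Virologic Suppression** needs a ≥0.5 log10 "decline and does suppress (< 50 copies) at any time after primary endpoint and does not have a" rise of that kind. It is the same as Suboptimal Response, except that the patient does fall below 50 copies.

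The section then promises "A table summarizing virologic outcome at the each key visit after Week 12" and a listing by patient. The listing shell (SAP section 6, headed At EOS) has three separate columns: the snapshot code, Virologic Failure and Virologic Success. Footnote [3] puts the first three labels under failure, and footnote [4] puts the last two under success. The programming note says which labels to print and gives no order.

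**The concern.** A set of outcome labels should give each patient exactly one. Here the failure label is fixed at Week 12, while the success labels look at the whole course with no deadline. Nothing in the available text says which prevails. The listing footnotes restate the definitions with different conditions. A programmer would have to choose between text and footnotes, and between failure and success, possibly after open-label data have been seen. At stake is how individual patients are described in the listing, and in the promised table if it uses these labels.

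**Working it through.** The plan states no figure to reproduce, so the check applies the definitions to example viral-load courses. Cohort 2 viral load is scheduled at Days 7 and 14 and Weeks 4, 6, 8, 12, 16, 20, 24, 28, 36 and 48 (Protocol Tables 3-5 and 3-6). Drop = log10(Baseline ÷ value); rise = log10(value ÷ nadir).

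**1. Late responder.** Baseline is 35,350 copies/mL, the TMB-301 median in Protocol 1.2, used only as an illustration. The other values are assumed.

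| Visit | Copies/mL | Drop (log10) |
|---|---|---|
| through Week 12 | 30,000 | log10(35,350/30,000) = 0.07 |
| Week 16 | 9,000 | log10(35,350/9,000) = 0.59 |
| Week 20 | 3,000 | log10(35,350/3,000) = 1.07 |
| Week 24 | 400 | log10(35,350/400) = 1.95 |
| Week 28 on | 40 | log10(35,350/40) = 2.95 |

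- Failure to achieve: met, since no drop reaches 0.5 by Week 12.
- Suppression: met, since the drop is ≥0.5, the value is below 50 and there is no rise from nadir.
- If the course levels off at 800 copies (drop log10(35,350/800) = 1.65), the second label is Suboptimal Response instead.
- One-decimal rounding (SAP 4.4) changes nothing. Baseline 4.5, then 4.5 through Week 12 (drop 0.0), then 4.0 at Week 16 (drop 0.5).
- Missing-equals-failure (MEF) imputation does not remove it. SAP 3.3.4 overwrites later values only after confirmed virologic failure, which SAP 2.1 defines as two consecutive drops <0.5 from Week 24. Here the drops at Weeks 24 and 28 are 1.95 and 2.95.

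**2. Footnotes against text.** Footnote [4] leaves out the ≥1 log10 rise exclusion.

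- Baseline 4.5, nadir 2.0 log10 (100 copies), then 3.5 twice. The rise is 3.5 − 2.0 = 1.5. By the text this is Rebound only; by the footnotes it is Rebound plus Suboptimal Response.
- 40 copies, then 500 and 600. The rises are log10(500/40) = 1.10 and log10(600/40) = 1.18. By the text this is Breakthrough only; by the footnotes it is Breakthrough plus Suppression.

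Footnote [3] also differs. It counts the rise in the second limb of Failure to achieve/maintain only after Week 12, and it adds to Rebound a requirement that the decline was maintained.

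**3. First decline exactly at Week 12, later lost.** Take Baseline 4.5, then 4.3 to Week 8 (drop 0.2), 3.8 at Week 12 (drop 0.7), 3.9 to Week 20, and 4.2 and 4.3 at Weeks 24 and 28 (drops 0.3 and 0.2).

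- The first limb is not met, because there is a decline by Week 12.
- The second limb is not met, because the decline is not before Week 12.
- Rebound is not met, because the rises are 4.2 − 3.8 = 0.4 and 4.3 − 3.8 = 0.5.
- If having a decline means ever having had one, the only label is Suboptimal Response, a success. If it means having one at the visit, there is no label. By SAP 2.1 the patient is a virologic failure.

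**4. Conditional cases.**

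- *Breakthrough with Suppression.* Two results ≥200 with a rise <1 log10 need the lower result to be under 10 × nadir, so the nadir must exceed 200/10 = 20 (22 if log10 values are rounded). At 40, then 300 and 350, the rises are 0.88 and 0.94 and both labels apply. If results below 50 are set to 20 or less, there is no overlap.
- *No label.* 12 copies, then 150 and 150. The rise log10(150/12) = 1.10 rules out Suppression, and 150 < 200 rules out Breakthrough. The other three labels also fail, given a decline by Week 12 that is kept.
- *Failure to maintain with Suboptimal Response.* Baseline 4.5, then 3.8 at Week 8, 3.9 to Week 20, 4.2 and 4.3 at Weeks 24 and 28. Both labels apply on the ever-had reading; on the at-the-visit reading it is a failure only.

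**The case against.** The strongest reply is that little depends on this. No formal hypothesis testing is planned (SAP 3.4.2), and the only visible output carrying the five labels is one descriptive listing. The late-responder pattern needs a Cohort 2 patient to miss 0.5 log10 at every scheduled measurement from Day 7 to Week 12. In TMB-301, 82.5% reached it within a week of the loading dose. Some table and listing shells are not in the available text, so a precedence rule there cannot be excluded. All of this stands. It limits the size of the point but does not make the definitions consistent.

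A second reply is that SAP 3.3.4 imputes failure at all visits after confirmed virologic failure, which suggests that failure is meant to prevail. That is fair for the lost-response examples. It does not reach the late responder, who never meets the virologic failure definition.

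A third reply is that the programming note uses the footnotes to show which labels to print, not to derive them. That also stands: footnote [4] adds labels only if the listing is programmed from it. Otherwise the printed footnotes misdescribe what was computed.

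A reader might infer more than this. One inference is that the promised table will double-count patients. Its layout is not available, and its wording echoes the snapshot paragraph, so it may report snapshot codes alone. Another is that Breakthrough always overlaps Suppression. That requires numeric values above about 20 for results below 50, which the documents do not give; Protocol 1.2 calls <50 the assay limit in an earlier study.

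**Conclusion.** The point holds as a minor one. Three defects follow from the SAP's own wording: the late-responder contradiction, the mismatch between the text and footnotes [3] and [4], and the gap at exactly Week 12. The first needs no assumption about assay values, rounding, MEF or how the decline is read; it needs only a first response after Week 12 and before failure is confirmed. The Breakthrough overlap and the no-label example depend on the numeric value given to results below 50. The overlap of Failure to maintain with the success labels depends on the ever-had reading.

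How many patients are affected cannot be derived from the documents. A reader might infer that the trial's efficacy results are in doubt, and the documents do not support that. The Day 7 primary endpoint (SAP 4.5.1), the snapshot codes and the response rates in SAP 4.5.2.1 and 4.5.2.2 have their own definitions. The effect is limited to the listing, and to the table if it uses these labels.

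**What to change.** Before analysis, amend SAP 4.5.2.3 and the listing shell:

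1. Make the categories exclusive, with a stated order in which failure precedes success, for example Breakthrough, Rebound, Failure to maintain, Failure to achieve, then Suppression or Suboptimal Response.
2. Report late responders (first ≥0.5 log10 decline after Week 12) as their own category. Restrict Failure to achieve to patients with no later decline, so that the new row is not emptied by the order. Say where a late responder who then loses response is counted.
3. Add a residual category for patients who meet none of the definitions.
4. Use the same Week 12 wording, by Week 12, in both limbs of Failure to achieve/maintain.
5. State whether the decline is ever achieved or present at the visit, which numeric value results below 50 take, whether one-decimal rounding enters the rise from nadir, and that MEF applies here.
6. Use identical definitions in the text and in footnotes [3] and [4], and say whether the promised table uses these labels.

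The cost is SAP wording and minor reprogramming, with no new data. The downside is one or two extra rows and a possibly lower success count.

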#### 4.5.2.4 CD4+ T-Cell Counts

Summary statistics will be presented for CD4+ T-cell count and change from Baseline in CD4+ T-cell count at the each key visit after Week 12 [Weeks 24, 48, 72, 96, 120, and 144/EOS].

CD4+ T-Cell Counts for all patients at all assessed visits will also be presented in a data listing. The listing will include a column indicating whether or not the patient met the definition of toxicity (2 consecutive laboratory results, at least 14 days apart, with a CD4+ T-cell count below

200 cells/mm^3 that also represents a 50% reduction from the Baseline CD4+ T-cell count).

## 4.5.3. Graphical Displays

In addition to the tables and listings described above, the following graphical displays of efficacy endpoints will also be included:

- Proportion of patients achieving a ≥ 0.5 log10 decrease from Baseline in viral load at all scheduled visits;
- Proportion of patients achieving  $a \ge 1.0 \log_{10}$  decrease from Baseline in viral load at all scheduled visits;
- Proportion of patients achieving RNA levels < 50 copies/mL at all scheduled visits;
- Proportion of patients achieving RNA levels < 400 copies/mL at each study visit;
- Mean (+/- SE) RNA levels (copies/mL) at all scheduled visits;
- Mean (+/- SE) change from Baseline in RNA levels (copies/mL) at all scheduled visits;
- Mean (+/- SE) CD4+ cell count (cells/mm^3) at all scheduled visits;
- Mean (+/- SE) change from Baseline in CD4+ T-cell count (cells/mm^3) at all scheduled visits.

## 4.6. Exploratory/Other Analyses

Summaries of viral resistance test results, immunogenicity results, and other virology results will be presented, prepared by TaiMed.

**CONFIDENTIAL** 

# **Notes Applicable to All Listings**

#### General Programming Notes:

- 1. There are a few listings that might fit as they are or might have to be split once we see the output with actual data.
- 2. All listings should start with and be sorted by Patient ID (concatenation of site number and patient number) and then visit date as appropriate.
- 3. If columns with specific text should be widened due to the amount of text, it is up to the programmer's discretion. However, please keep to the industry standard margin of 1 inch on bottom and sides and 1.25 inches on the top. Font is Courier New 8 point.
- 4. For all dates used, character format dates to capture partial dates. Use dashes where a month or day is missing. If entire date is missing just leave blank. i.e., JAN2011 or 01-2011.
- 5. If a programming note appears on the mock listing indicating that the footnote should appear only on the first page, this means the first page of output contains all footnotes and ONLY footnotes. All subsequent pages contain data with one footnote that says "Refer to page 1 for footnotes".
- 6. Some of the mock tables display numbers rather than x's. The numbers are meaningless and are for example only. Where visit names are displayed in tables, these are examples as well. Correct visit names for the TMB-311 study should be displayed in the actual output.
- 7. Each listing should include all applicable data, even if only a subset of the full set of treatment groups is displayed in the mocks. And unlike the tables and graphs, the listings should also include the 2 PI-IND rollover patients.
- 8. Sort each listing by Treatment and then Patient ID where applicable.

Listing 16.2.1.1

Patient Disposition

Treatment	Patient ID Sc	reened	ITT Population [1]	SAF Population [2]	
C1:301/800mg	311-XX-XXX	YES	YES	YES	
C1:202/800mg	311-XX-XXX	YES	YES	YES	
C1:202/2000mg	311-XX-XXX	YES	YES	YES	
C2:800mg	311-XX-XXX	YES	YE:	S YES	

Intent-to-Treat (ITT) Population consists of all patients enrolled into the study.

Programming note: Add the mITT population if analyst decides it is needed later.

Westat (Created on DDMMYYYY)
S:\TMB311\DA\SAS\L PATDISP.SAS

Safety (SAF) Population consists of patients receiving at least one partial dose of study drug.

Listing 16.2.1.2 Study Discontinuation

## Listing 16.2.2.2 Protocol Violations

Treatment	Patient		Protocol	Details	Approval	Date of
	ID	Visit	Violation Code	of Violation	Obtained	Approval
C1:202/800mg	311-XX-XXX	XXXXXX	XXX	XXXXXXXXXX	Yes/No	DDMONYYYY
C1:202/2000mg	311-XX-XXX	XXXXXX	XXX	XXXXXXXXX	Yes/No	DDMONYYYY

Westat (Created on DDMMMYYYY)
S:\TMB311\DA\SAS\L\_PROTVIOS.SAS

TaiMed Biologics, Inc. TMB-311

## Listing 16.2.4.2 Medical History

Treatment	Patient ID	Medical Condition/Surgery	Start Date	Stop Date
C1:301/800mg	311-xx-xxx	xxxxxxxxxxxx	DDMONYYYY	DDMONYYYY or ONGOING
C2:800mg	311-xx-xxx	xxxxxxxxxxxx	DDMONYYYY	DDMONYYYY or ONGOING

## Listing 16.2.5.1 Study Drug Administration

					Start Time S		:		Starting	Ending	Was entire	
	Patient		Visit		of Infusion	Infusion		Infusion	Volume	Volume	dose	
Treatment	ID	Visit	Date	Dose (mg)	(hh:mm)	(hh:mm)	Infusion Site	Side	(ml)	(ml)	delivered?	Reason if No or Interrupted
C1:301/800m	311-XX-XXX	xxxxxx	DDMONYYYY	2000/800	XX:XX	XX:XX	Cephalic Vein/Other Vein	Left/	xxx	xxx	Yes/No/Yes w/ Interruption	xxxxxxxx
		XXXXXX	DDMONYYYY	2000/800	xx:xx	XX:XX		Right				
							Cephalic Vein/Other Vein	Left/	xxx	xxx	Yes/No/Yes w/ Interruption	
								Right				
C2:800mg	311-XX-XXX	xxxxxxx	DDMONYYYY	2000/800	xx:xx	XX:XX	Cephalic Vein/Other Vein	Left/	xxx	xxx	Yes/No/Yes w/ Interruption	xxxxxxxxx
								Right				

Listing 16.2.5.2 ART Exposure

Treatment	Patient ID	Medication	Standardized Medication Name [1]	Indication	Start Date	Stop Date	Dose	Unit	Route	Frequency
C1:202/2000 mg	311-XX- XXX	xxxxxxx	xxxxxxx	xxxxxxx	DDMONYYYY	DDMONYYYY Or ONGOING	xxxx	xxxx	xxxxx	xx
C2:800mg	311-xx- xxx	xxxxxxx	xxxxxxx	xxxxxxx	DDMONYYYY	DDMONYYYY Or ONGOING	xxxx	xxxx	xxxxx	хх

 Medications were coded with WHO Drug Dictionary Version March, 2014.

Westat (Created on DDMMMYYYY)
S:\TMB311\DA\SAS\L\_ARTEXP.SAS

Listing 16.2.5.3 Previous and Concomitant Medications

Treatment	Patient ID	Medication	Standardized Medication Name [1]	Indication	Start Date	Stop Date	Dose	Unit	Route	Frequency
					DDMONYYYY	DDMONYYYY				
C1:202/800 mg	311-xx-xxx	xxxxxxx	xxxxxxx	xxxxxxx		Or ONGOING	xxxx	xxxx	xxxxx	xx
						DDMONYYYY				
C2:800mg	311-XX-XXX	xxxxxxx	xxxxxxx	xxxxxxx	DDMONYYYY	Or ONGOING	xxxx	xxxx	xxxxx	xx

 Medications were coded with WHO Drug Dictionary Version March, 2014.

Westat (Created on DDMMMYYYY)
S:\TMB311\DA\SAS\L\_CONMED.SAS

## Listing 16.2.5.4 Concomitant Procedures

	Patient ID	Procedure	Procedure Date	Reason
Treatment				
C1:301/800mg	311-xx-xxx	xxxxxxx	DDMONYYYY	xxxxxxx
C2:800mg	311-xx-xxx	XXXXXXX	DDMONYYYY	xxxxxxx

Westat (Created on DDMMMYYYY)
S:\TMB311\DA\SAS\L\_CONPROCS.SAS

Listing 16.2.5.5 Optimized Background Regimen (OBR)

Treatment	Patient ID	Medication	Standardized Medication Name [1]	Indication	Start Date	Stop Date	Dose	Unit	Route	Frequency	Reason for Change
					DDMONYYYY	DDMONYYYY					
C1:301/800m g	311-XX- XXX	xxxxxxx	xxxxxxx	xxxxxxx		Or ONGOING	xxxx	xxxx	xxxxx	xx	xxx
						DDMONYYYY					
C2:800mg	311-XX- XXX	xxxxxxx	xxxxxxx	xxxxxxxx	DDMONYYYY	Or ONGOING	xxxx	xxxx	xxxxx	ХХ	xxx

Medications were coded with WHO Drug Dictionary Version March, 2014.

Westat (Created on DDMMMYYYY)
S:\TMB311\DA\SAS\L\_OBR.SAS

Listing 16.2.5.6 Optimized Background Regimen (OBR) Adherence

	Patient			Has the patient taken all required doses of OBR					
Treatment	ID	Visit	Visit Date	since the last visit?	If No Explain				
C1:202/800mg	::202/800mg 311-XX-XXX XXXXX DDMONYYYY		DDMONYYYY	YES/NO	xxxxxxxxxx				
C1:202/2000mg		xxxx	DDMONYYYY	YES/NO	xxxxxxxxxxx				

Westat (Created on DDMMMYYYY)
S:\TMB311\DA\SAS\L\_OBRADHER.SAS

Listing 16.2.6.1 Post-Injection Observation

					Start Time of Observation	End Time of Observation	
Treatment	Patient ID	Visit	Visit Date	Observed After Study Drug	(hh:mm)	(hh:mm)	Comments
C1:301/800mg	311-xx-xxx	xxx	DDMONYYYY	YES/NO	xx:xx	XX:XX	xxxxxxxxxxxxxx
C2:800mg	311-xx-xxx	xxx	DDMONYYYY	YES/NO	xx:xx	xx:xx	xxxxxxxxxxxxxxx

Westat (Created on DDMMMYYYY)
S:\TMB311\DA\SAS\L\_POSTINJECT.SAS

